4.4.2 Dose Modifications

Dose reductions or dose escalations are not permitted. All dose modification rules apply to both Arms A and B given the blinded nature of this study.

4.4.3 Criteria to Resume Treatment

Subjects should resume treatment with nivolumab and ipilimumab in both arms A and B given the blinded nature of the study when the drug-related AE(s) resolve(s) to Grade ≤ 1 or baseline, with the following exceptions:

- Subjects may resume treatment in the presence of Grade 2 fatigue
- Subjects who have not experienced a Grade 3 drug-related skin AE may resume treatment in the presence of Grade 2 skin toxicity
- Subjects with Grade 2 AST/ALT or total bilirubin may resume treatment when laboratory values return to baseline and management with corticoids, if needed, is completed.
- Subjects with combined Grade 2 AST/ALT AND total bilirubin values meeting discontinuation parameters (Section 4.4.1) should have treatment permanently discontinued

- Drug-related pulmonary toxicity, diarrhea, or colitis must have resolved to baseline before treatment is resumed. Subjects with persistent Grade 1 pneumonitis after completion of a steroid taper over at least 1 month may be eligible for retreatment if discussed with and approved by the BMS Medical Monitor.
- Drug-related endocrinopathies adequately controlled with only physiologic hormone replacement may resume treatment after consultation with the BMS Medical Monitor. Adrenal insufficiency requires discontinuation regardless of control with hormone replacement.

If the criteria to resume treatment are met, the subject should restart treatment at the next scheduled time point per protocol. However, if the treatment is delayed past the next scheduled time point per protocol, the next scheduled time point will be delayed until dosing resumes.

If treatment is delayed > 6 weeks, the subject must be permanently discontinued from study therapy, except as specified in [Section 4.4.1](#).

4.4.4 Discontinuation Criteria

All discontinuation criteria apply for nivolumab and ipilimumab in both Arms A and B (during Part 1) given the blinded nature of this study.

Treatment should be permanently discontinued for the following:

- Any Grade 2 drug-related uveitis, eye pain or blurred vision that does not respond to topical therapy and does not improve to Grade 1 severity within the re-treatment period OR requires systemic treatment.
- Any Grade 3 non-skin, drug-related adverse event lasting > 7 days or recurs, with the following exceptions for laboratory abnormalities, drug-related uveitis, pneumonitis, bronchospasm, diarrhea, hypersensitivity reactions, infusion reactions and endocrinopathies:
 - Grade 3 drug-related uveitis, pneumonitis, bronchospasm, diarrhea, colitis, neurologic toxicity, hypersensitivity reaction, or infusion reaction of any duration requires discontinuation
 - Grade 3 drug-related endocrinopathies adequately controlled with only physiologic hormone replacement do not require discontinuation. Adrenal insufficiency requires discontinuation, regardless of control with hormone replacement.
 - Grade 3 drug-related laboratory abnormalities do not require treatment discontinuation except:
 - Grade 3 drug-related thrombocytopenia > 7 days or associated with bleeding requires discontinuation
 - Any drug-related liver function test (LFT) abnormality that meets the following criteria require discontinuation:
 - Grade ≥ 3 drug-related AST/ALT or Total Bilirubin abnormality
 - Concurrent AST or ALT > 3 x ULN and total bilirubin > 2 x ULN
- In most cases of Grade 3 AST or ALT elevation, study drugs) will be permanently discontinued. If the investigator determines a possible favorable risk/benefit ratio that warrants

continuation of study drug(s), a discussion between the investigator and the BMS Medical Monitor/designee must occur.

- Any Grade 4 drug-related adverse event or laboratory abnormality (including, but not limited to creatinine, AST, ALT, or total bilirubin), except for the following events which do not require discontinuation:
 - Grade 4 neutropenia \leq 7 days
 - Grade 4 lymphopenia or leucopenia
 - Isolated Grade 4 amylase or lipase abnormalities that are not associated with symptoms or clinical manifestations of pancreatitis.
 - Isolated Grade 4 electrolyte imbalances/abnormalities that are not associated with clinical sequelae and are corrected with supplementation/appropriate management within 72 hours of their onset
 - Grade 4 drug-related endocrinopathy adverse events, such as hyper- or hypothyroidism, or glucose intolerance, which resolve or are adequately controlled with physiologic hormone replacement (corticosteroids, thyroid hormones) or glucose-controlling agents, respectively, may not require discontinuation after discussion with and approval from the BMS Medical Monitor.
- Any event that leads to delay in dosing lasting $>$ 6 weeks from the previous dose requires discontinuation, with the following exceptions:
 - Dosing delays to allow for prolonged steroid tapers to manage drug-related adverse events are allowed.
 - Dosing delays lasting $>$ 6 weeks from the previous dose that occur for non-drug-related reasons may be allowed if approved by the BMS medical monitor.
- Prior to re-initiating treatment in a subject with a dosing delay lasting $>$ 6 weeks, the BMS medical monitor must be consulted. Tumor assessments should continue as per protocol even if dosing is delayed. Periodic study visits to assess safety and laboratory studies should also continue every 6 weeks or more frequently if clinically indicated during such dosing delays.
- Any adverse event, laboratory abnormality, or intercurrent illness which, in the judgment of the Investigator, presents a substantial clinical risk to the subject with continued nivolumab dosing.

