4.4.1 Dose Delay Criteria

Regardless of whether or not the event is attributed to nivolumab, ipilimumab, or both, all study drugs must be delayed until treatment can resume (See Section 4.4.3). Tumor assessments for all subjects should continue as per protocol even if dosing is delayed.

Nivolumab and ipilimumab administration should be delayed for the following:

- Grade ≥ 2 non-skin, drug-related adverse event, with the exception of fatigue or laboratory abnormalities that do not require a treatment delay.
- Grade 2 drug-related creatinine, AST, ALT or Total Bilirubin abnormalities
- Grade 3 skin, drug-related adverse event
- Grade 3 drug-related laboratory abnormality, with the following exceptions :
 - Grade 3 lymphopenia does not require dose delay
 - If a subject has a baseline AST, ALT or total bilirubin that is within normal limits, delay dosing for drug-related Grade ≥ 2 toxicity
 - Grade ≥ 3 AST, ALT, or total bilirubin will require discontinuation
 - Any Grade ≥ 3 drug-related amylase or lipase abnormality that is not associated with symptoms or clinical manifestations of pancreatitis does not require dose delay.
- Any adverse event, laboratory abnormality, or intercurrent illness which, in the judgment of the investigator, warrants delaying the dose of study medication.

Subjects requiring delay should be re-evaluated weekly or more frequently if clinically indicated and resume dosing when re-treatment criteria are met.

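### Drug-related Grade 3 AST/ALT elevation is a mandatory permanent stop in two places in the protocol and a discretionary one in a third, with nothing to say which governs

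*Protocol*

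**What the plan says.** **Grade 3 AST/ALT.** Three statements in the protocol apply.

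- Section 4.4.1 (Dose Delay Criteria), under drug-related Grade 3 laboratory abnormalities: "Grade ≥ 3 AST, ALT, or total bilirubin will require discontinuation". No exception is given.
- Section 4.4.4 (Discontinuation Criteria), lead-in to the liver criteria: "Any drug-related liver function test (LFT) abnormality that meets the following criteria require discontinuation". The first criterion listed is "Grade ≥ 3 drug-related AST/ALT or Total Bilirubin abnormality".
- Section 4.4.4, the bullet that follows: "In most cases of Grade 3 AST or ALT elevation, study drugs) will be permanently discontinued". If the investigator sees a possible favorable balance of risk and benefit that supports "continuation of study drug(s), a discussion between the investigator and the BMS Medical Monitor/designee must occur".

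**Adrenal insufficiency and other endocrinopathies.** Under the Grade 3 rule, Section 4.4.4 says: "Adrenal insufficiency requires discontinuation, regardless of control with hormone replacement". Section 4.4.3 (Criteria to Resume Treatment) says the same without naming a grade. Later in 4.4.4, Grade 4 endocrinopathies may escape discontinuation, with the medical monitor's approval, if they resolve or are "adequately controlled with physiologic hormone replacement (corticosteroids, thyroid hormones") or with glucose-controlling agents. The thyroid and glucose events named there are given as examples. Adrenal insufficiency is neither named nor excluded.

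**The concern.** A permanent-stop rule has to give one answer for one event. A site facing a drug-related Grade 3 ALT elevation finds two sentences that leave no choice and one that does. The first consequence is for patient safety: these rules apply to both blinded arms, and the protocol has no data monitoring committee (Section 7), so sites depend on the written rule.

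The second consequence is for the data. Which sentence a site follows decides whether the subject receives further combination doses and whether the subject enters Part 2. That feeds several planned summaries in the SAP: exposure (Section 7.4.1), reasons for stopping treatment (7.3.1), adverse events leading to discontinuation (7.6.4) and the population of All Subjects Treated in Part 2 (6.3). Differences between sites in these outputs could then reflect how the text was read rather than how the drug was tolerated.

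**Working it through.** No figure is involved, so the check is a side-by-side reading of Sections 4.4.1, 4.4.3 and 4.4.4.

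1. **Drug-related Grade 3 AST/ALT.**
   - 4.4.1: must stop, no exception.
   - 4.4.4, liver criteria: must stop, no exception.
   - 4.4.4, following bullet: usually stop; continuation possible after a discussion.
   - Result: direct conflict. A subject who continues under the third statement breaches the first two.

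2. **Is the third statement marked as an exception?** Elsewhere in these sections the protocol announces its exceptions explicitly. This bullet does not refer to the liver criteria or to 4.4.1, and it omits the drug-related qualifier that the liver criteria carry. It asks only for a discussion, whereas the Grade 4 endocrine exception also asks for the medical monitor's approval. Whether the monitor can refuse is therefore not stated.

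3. **What happens to a subject who continues?** Section 4.4.3 has a liver-specific resumption rule for Grade 2 AST/ALT and none for Grade 3.

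4. **Endocrinopathies other than adrenal insufficiency, controlled with hormone replacement.**
   - Grade 3 (4.4.4): no stop required.
   - Resumption (4.4.3): allowed after consultation.
   - Grade 4 (4.4.4): may continue, with approval.
   - Result: no conflict. The conditions tighten as the grade rises.

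5. **Grade 4 adrenal insufficiency on corticosteroid replacement.**
   - 4.4.3, no grade given: must stop.
   - 4.4.4, adrenal sentence: must stop, but it is placed under the Grade 3 rule.
   - 4.4.4, Grade 4 exception: may continue with approval, if this open-ended exception is taken to include adrenal insufficiency.
   - Result: possible conflict, resting on the open list of examples and the mention of corticosteroids.

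6. **Effect on the primary endpoint.** Protocol Section 8.3.1 and SAP Section 4.1 count a subject once, for at least one drug-related AE of Grade 3 or higher with onset from first dose to 30 days after last dose. A subject whose hepatic or adrenal event meets that definition is already counted. Stopping or continuing afterwards does not alter that.

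**The case against.** The best defense is that the third AST/ALT statement comes straight after the liver criteria, in the section designated for discontinuation, and has no purpose except as an exception for Grade 3 AST/ALT. Its indentation in the source cannot be judged from extracted text, so its status as a separate bullet proves little. Section 4.4.1 is about delays, and Section 3.5 sends the reader to 4.4.4 for discontinuation. Much of this stands: an intended exception is a plausible reading of 4.4.4. But the unqualified sentence in 4.4.1 would still contradict it, and nothing says that 4.4.4 prevails.

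On adrenal insufficiency, the defense is that a specific rule, stated twice, naturally prevails over a general exception that needs approval. That is a reasonable reading and is why this limb is secondary. The text does not state the precedence.

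A reader might also infer more than the documents support:

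- **That the endocrine rules as a whole conflict, or treat Grade 4 more leniently than Grade 3.** Steps 4 and 5 confine any conflict to adrenal insufficiency. For other controlled events Grade 4 carries the extra condition of approval.
- **That uneven stopping distorts the primary comparison by lengthening the time at risk.** The endpoint is binary and these subjects already count. The rules are the same in both blinded arms, and no route to bias between arms is shown.
- **That the planning rates of 40% and 55% indicate how many subjects are affected.** Those are assumed rates of all drug-related Grade 3-5 AEs (Protocol Section 8.1) and say nothing about hepatic or adrenal events.

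**Conclusion.** The Grade 3 AST/ALT conflict is real, and the text should be corrected: a site cannot follow all three statements. Grade 4 adrenal insufficiency is a lesser ambiguity that rests on inference. Other endocrinopathies need no change on this ground.

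The effect is on patient safety and on consistent exposure, discontinuation and entry to Part 2 across sites. Its size cannot be given, because the documents state no rate for either event. The planned primary test and sample size are not called into question.

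Two limits apply. The statement about the primary outcome covers events that already fall within the 30-day window. In the planned six-week gap before Part 2 (6 × 7 = 42 days), an event with onset on days 31 to 42 would count only if a later dose were given. The documents give no basis for sizing that case, and the point does not rest on it. Second, the management algorithms in Appendix 3 were not in the text available, so whether they clarify the rules could not be checked.

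**What to change.** Reconcile Protocol Sections 4.4.1, 4.4.3 and 4.4.4 so that each event has one rule:

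- For Grade 3 AST/ALT, give a single statement and have the other sections refer to it. If continuation is meant to be possible, write the exception inside that rule, name what it overrides, and say whether discussion is enough or approval is needed.
- For adrenal insufficiency, say whether the Grade 4 endocrine exception covers it.
- Correct the nearby cross-references. Section 4.4.3 cites 4.4.1 for the combined AST/ALT and bilirubin criterion and for the exceptions to the six-week delay limit, but both are in 4.4.4. In 4.4.1, the delay instruction for Grade 2 and above overlaps the stop instruction for Grade 3 and above.
- Check Appendix 3 against the result.

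Which rule applies is for the sponsor's medical team to decide. The cost is a protocol clarification and a notice to sites. No change to the analysis plan or sample size is needed.

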4.3.2 Part 2 Study Drug Administration (Maintenance)

Starting 6 weeks after the last co-administered dose in Part 1, subjects will be administered a flat dose 480 mg nivolumab IV as a 30-minute IV infusion every 4 weeks (Q4W) (\pm 3 days) until unacceptable toxicity or disease progression, up to a maximum of 2 years treatment.

Subjects may be dosed up to 3 days after the scheduled date if necessary. Subsequent dosing should be based on the actual date of administration of the previous dose of drug. Every effort should be made to adhere to protocol treatment schedule of administration of nivolumab every 4 weeks in the maintenance phase. In extenuating circumstances in which the patient cannot make the dosing schedule within the 3-day window, BMS Monitor should be contacted.

For details on prepared drug storage, preparation, and administration, please refer to the BMS-936558 (nivolumab) IB, the ipilimumab IB and/or pharmacy reference sheets.

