4.5 Selection and Timing of Dose for Each Subject

The dosing regimen and schedule for Parts 1 and 2 are detailed in Table 4.5-1 and Table 4.5-2, respectively.

Note: The first flat dose 480 mg nivolumab in Part 2 will be administered 6 weeks after the last combination dose in Part 1.

Table 4.5-1: Dosing Schedule for Part 1 (Double-Blinded)				
Every 3 weeks dosing 1 cycle = 3 weeks				
	Cycle 1	Cycle 2	Cycle 3	Cycle 4
Arm A	Nivolumab 3 mg/kg Ipilimumab 1 mg/kg	Nivolumab 3 mg/kg Ipilimumab 1 mg/kg	Nivolumab 3 mg/kg Ipilimumab 1 mg/kg	Nivolumab 3 mg/kg Ipilimumab 1 mg/kg
Arm B	Nivolumab 1 mg/kg Ipilimumab 3 mg/kg	Nivolumab 1 mg/kg Ipilimumab 3 mg/kg	Nivolumab 1 mg/kg Ipilimumab 3 mg/kg	Nivolumab 1 mg/kg Ipilimumab 3 mg/kg

Table 4.5-2: Dosing Schedule for Part 2 (Open Label)	
Every 4 weeks dosing 1 cycle = 4 weeks, Cycle 5 to begin 6 weeks after Cycle 4 ^a	
	Cycle 5 and beyond
Arms A and B	Flat dose 480 mg nivolumab

^a Cycle X - Cycle 8, 9, etc until disease progression or unacceptable toxicity or a maximum treatment of 2 years.

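### The six-week limit in Protocol Section 4.4.4, read literally, leaves no slack at Cycle 5, which is itself due six weeks after Cycle 4, and Sections 4.4.1, 4.4.3 and 4.4.4 do not give one answer for a delayed Cycle 5

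*Protocol*

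**What the plan says.** **The limit.** Protocol Section 4.4.4 provides that an event delaying dosing for more than "6 weeks from the previous dose requires discontinuation, with the following exceptions". There are two exceptions. The first reads "Dosing delays to allow for prolonged steroid tapers to manage drug-related adverse events are allowed". The second covers delays for reasons unrelated to study drug, if the medical monitor approves. The monitor must also be consulted before treatment restarts after a delay of more than six weeks.

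**The schedule.** Part 2 begins "Starting 6 weeks after the last co-administered dose in Part 1" (Section 4.3.2). Section 4.5 agrees: "The first flat dose 480 mg nivolumab in Part 2 will be administered 6 weeks after the last combination dose in Part 1". The synopsis and Section 3.1.2 give the same interval. Doses are three weeks apart within Part 1 and four weeks apart within Part 2. Section 4.3.2 accepts a dose up to three days after its scheduled date. In extenuating circumstances, where the patient "cannot make the dosing schedule within the 3-day window, BMS Monitor should be contacted".

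**Hold and resume.** Section 4.4.1 makes the hold mandatory for listed events, among them "Grade 3 skin, drug-related adverse event", and adds: "Subjects requiring delay should be re-evaluated weekly or more frequently if clinically indicated and resume dosing when re-treatment criteria are met". Section 4.4.3 says to resume on recovery. If the delay runs past the next scheduled time point, "the next scheduled time point will be delayed until dosing resumes". Section 4.4.3 has its own permanent stop for treatment delayed by more than six weeks. It does not say when the six weeks start, and it points to Section 4.4.1 for exceptions.

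**Scope.** The opening sentence of Section 4.4.4 applies its criteria to both drugs in both arms, with a parenthesis naming Part 1. Section 3.5 refers to 4.4.4 without that restriction.

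**The concern.** A limit measured from the previous dose allows a delay equal to the limit minus the scheduled interval. At Cycle 5 the scheduled interval already equals the limit. A short drug-related hold there, fully recovered, would be a permanent stop on the literal text of 4.4.4, while a hold of the same length at any other cycle would not.

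Two examples show how this arises. A Grade 2 AST or ALT rise must be held under 4.4.1 and may resume under 4.4.3 once values return to baseline, with corticoid management completed only if it was needed. A Grade 3 skin event must also be held, but the Grade 3 stopping rule in 4.4.4 is confined to non-skin events. If neither subject needs a prolonged taper, neither exception applies.

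At stake are who receives Part 2 nivolumab and whether sites treat the same situation alike. One site could follow the resume instruction in 4.4.3 and another the limit in 4.4.4, each relying on a sentence of the protocol.

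**Working it through.** The plan states no slack figure, so the check is calendar arithmetic on its own intervals.

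**1. Inputs.** Limit: 6 weeks = 42 days from the previous dose (4.4.4). Scheduled intervals: 21 days in Part 1, 42 days from Cycle 4 to Cycle 5, 28 days from Cycle 6 on (synopsis, 4.3.2, 4.5). Dosing window: up to 3 days late (4.3.2). Re-evaluation of held subjects: at least weekly (4.4.1).

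**2. Slack and its consequences.** Slack = 42 - scheduled interval. Days since the previous dose at the first weekly re-check, counted from the due date = interval + 7. Latest dose if the six weeks in 4.4.3 run from the due date = interval + 42.

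| Dose | Interval | Slack under 4.4.4 | First weekly re-check | Latest dose, 4.4.3 from due date |
|---|---|---|---|---|
| Cycles 2-4 | 21 | 42 - 21 = 21 | 28 | 63 |
| Cycle 5 | 42 | 42 - 42 = 0 | 49 | 84 |
| Cycle 6 on | 28 | 42 - 28 = 14 | 35 | 70 |

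Only Cycle 5 is past 42 days at the first re-check. A Cycle 5 dose given 1 to 3 days late, inside the window in 4.3.2, is already at 43 to 45 days. The text does not say whether such a dose counts as delayed; the point does not depend on it.

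**3. Exceptions.** A drug-related delay cannot use the exception for unrelated reasons. Without a prolonged taper it cannot use the steroid exception either. Consulting the monitor before a restart is a procedural step and does not create a third exception.

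**4. Cross-reference.** Section 4.4.3 sends the reader to 4.4.1 for exceptions to its six-week stop. Section 4.4.1 contains none; they are in 4.4.4.

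**5. Primary endpoint.** Take Cycle 1 as day 0, with no earlier delay. Cycle 4 falls on day 3 x 21 = 63, and Cycle 5 is due on day 63 + 42 = 105. If Cycle 4 remains the last dose, the 30-day window in Section 8.3.1 ends on day 63 + 30 = 93. An event starting on days 94 to 105, that is 31 to 42 days after Cycle 4, counts only if Cycle 5 is later given. This is a band of 105 - 94 + 1 = 12 days. It changes a subject's result only if that event is the sole qualifying drug-related Grade 3-5 event.

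Section 4.4.4 also stops most such events whatever the clock: Grade 3 non-skin events that last more than 7 days or recur, several Grade 3 events of any duration, Grade 3 or higher AST, ALT or bilirubin (with a discussion route for Grade 3 AST or ALT), and most Grade 4 events. What remains is mainly Grade 3 skin events, short Grade 3 non-skin events, some laboratory abnormalities and controlled endocrinopathies. Grade 2 liver abnormalities cannot count at all. The event is recorded either way, because collection runs to 100 days after the last dose (Section 6.2.1).

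**The case against.** **A specific cap on a general rule is normal drafting.** Sections 4.4.1 and 4.4.3 say when to hold and resume, and 4.4.4 limits the result. On that view the cap is merely tight at Cycle 5, and how tight it should be is the sponsor's clinical choice. The second part stands. The first does not settle the matter, because 4.4.3 contains a six-week stop of its own without a clock start. The two stops can differ by 84 - 42 = 42 days at Cycle 5.

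**The six weeks may measure the delay itself.** Section 4.4.3, and the sentence in 4.4.4 on consulting the monitor, both omit any mention of the previous dose. Under that reading the problem disappears and Cycle 5 could be given up to 84 days after Cycle 4. It requires setting aside the reference to the previous dose, which 4.4.4 uses both in the rule and in its second exception.

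**The Part 1 parenthesis may exclude Cycle 5.** If so, the limit does not reach Cycle 5, but Part 2 is then left without a stated 4.4.4 rule. The parenthesis may only explain why the criteria cover both drugs. Section 3.5 cites 4.4.4 without limit, and the last 4.4.4 criterion speaks of continued nivolumab dosing. The scope is unclear on either view.

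**The monitor will sort it out.** The contacts in 4.3.2 and 4.4.4 do reduce divergent handling. Neither states a stopping rule for a drug-related delay at Cycle 5.

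**Stronger readings a reader might infer.** One is that every late Cycle 5 ends treatment. The documents do not support this: prolonged tapers are exempt, and delays unrelated to study drug can be approved. Another is that the primary comparison is biased or one arm is favoured. Nothing in the documents gives the number of affected subjects or a difference between arms.

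**Conclusion.** The point holds as a conflict within the current protocol text. On the literal wording of 4.4.4, slack is 0 days at Cycle 5, 21 days within Part 1 and 14 days within Part 2. For a drug-related Cycle 5 delay without a prolonged taper, the sections can be read to give a permanent stop, a resumption up to 84 days after Cycle 4, or no applicable 4.4.4 rule.

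The consequence is for Part 2 exposure and consistency between sites, partly mitigated by monitor contact. The effect on the primary endpoint is minimal; that statement concerns the event causing the delay. The number of subjects cannot be derived, since it depends on which delays involve a prolonged taper, and the management algorithms in Appendix 3 are not in the text reviewed here.

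The arithmetic assumes six weeks means 42 days and, for the endpoint band, no earlier delays. No view is taken on which stopping rule is right.

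**What to change.** Reconcile Sections 4.3.2, 4.4.1, 4.4.3, 4.4.4 and 4.5 so that they give one answer for a delayed Cycle 5. Specifically:

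- state one clock start for the six weeks, and use it in both 4.4.3 and 4.4.4;
- state whether 4.4.4 applies in Part 2;
- correct the cross-reference in 4.4.3 so that it points to the section that holds the exceptions.

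The threshold itself is for the sponsor to set, and none is proposed here. The cost is a protocol clarification. It adds no patients, visits or data.
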